PROSPECTIVE RANDOMIZED COMPARISON OF 2 URETERAL ACCESS SHEATHS DURING FLEXIBLE RETROGRADE URETEROSCOPY

PI: [name]

Introduction

Ureteral access sheaths provide effective and reliable access during flexible ureteroscopy, and have demonstrated numerous advantages. Access sheaths have been shown to optimize success of flexible ureteroscopy, decrease operative time and cost, and minimize morbidity [1]. Technological advancements in ureteral access sheath design have significantly improved physical properties that have led to reduced failure rates and complications, however, the general design of access sheaths has remained similar for some time until recently. New designs, though commercially available, have a paucity of data comparing different models.

Background and Significance

After gaining initial ureteral access with a guidewire, access sheaths are typically back-loaded onto the safety guidewire through the inner lumen of the dilator, allowing for gradual ureteral dilation and smooth access to the upper collecting system. Until the recent development of Re-Trace™ (Coloplast) and Flexor Parallel™ (Cook Urological), guidewires would remain within the inner lumen of the access sheath after removal of the dilator, requiring additional instruments to pass directly alongside the guidewire as they are advanced through the sheath. These devices have now been designed with a slit on the dilator that guides the wire outside of the sheath, leaving the guidewire to remain parallel but exterior to the sheath as the dilator is removed. This design limits the need to place an additional working wire, and provides a clear working channel through the lumen of the sheath. A clear working channel is likely to increase irrigation flow for improved visibility, reduce intrarenal pressures, and help minimize interference between delicate ureteroscopes, baskets, and guidewires.

A recent prospective study by Doizi et al [2] evaluating the ability of the Re-Trace™ to gain ureteral access with the use of a single safety guidewire demonstrated good insertion rates and validated the effectiveness of the design, however, no study to date has systematically evaluated the impact of the design on ureteral trauma or provided a comparative analysis between commercially available devices incorporating this design.

We propose this randomized study to evaluate the effectiveness and safety of current commercially approved devices integrating this design (Re-Trace™ and Parallel™).

Purpose and Objectives

The primary objective of this study will be to evaluate the ability for 2 different ureteral access sheaths to obtain and maintain access to the upper collecting system, as well as evaluate ureteral injury using standardized 5-point classification system.

Secondary endpoints will include evaluating ease of instrument passage, stone extraction, device placement, and radiopacity.

Hypothesis

We hypothesize that the modified designs of Re-Trace and Parallel devices will demonstrate similar safety profiles.

Research method

The proposed study is a prospective randomized controlled trial comparing the safety and efficacy of ureteral access sheaths used in flexible ureteroscopy.

Patients scheduled for flexible ureteroscopy will be identified by the investigator at clinic visits or hospital admission at Cleveland Clinic. The research coordinator will approach patients to determine the patient's initial interest in research, and if interested, the consent process will be initiated prior to surgery.

In order to be eligible the patient must be a suitable operative candidate for flexible ureteroscopy and have an abdominopelvic computed tomography (CT) to delineate pre-operative stone size, with measurements captured in greatest axial and coronal dimensions. Patients who have had prior ipsilateral upper urinary tract reconstructive procedures, ureteral stricture, ureteral malignancy, or impacted ureteral stones will be excluded. Pregnant subjects will also be excluded.

Ureteroscopic treatment of renal calculi is a standard of care treatment approach, and participating in this study will not deviate from standard of care ureteroscopy procedures, however, procedures specific to the research will involve being randomized to the use of one of two ureteral access sheaths:

1. Coloplast Re-Trace
2. Cook Flexor Parallel

Choice of sheath length will be left to the discretion of the surgeon based on body habitus and site of pathology, while sheath diameter will be standardized to 12/14F. Smaller diameter sheaths (11/13F, 10/12F) will be used if significant resistance occurs during advancement, otherwise patients will be excluded from the study if unable to gain ureteral access, or if ureteral balloon dilation or semi-rigid ureteroscopy is required to gain ureteral access.

If unable to obtain access with the initial sheath the patient is randomized to, the patient will be randomized to a backup sheath. If unable to obtain access with backup sheath, then a second backup sheath will be used. If unable to obtain access with any of the three sheaths with diameter 12/14F, an attempt will be made with up to three additional sheaths of a similar smaller diameter (11/13F or 10/12F), in a random order. If access has not been obtained after randomization to 6 sheaths, the patient will be considered a failure and it will be the surgeon's discretion to either place a stent and do a staged second look at a later time, proceed with ureteroscopy without a sheath, or balloon dilate.

Pre-operative data collection will include age, race, gender, ASA (American Society of Anesthesiologists) score (for comorbidity assessment), body mass index (BMI), and disease history, including stone disease, prior ureteroscopic procedures, vascular disease, and pelvic radiation. Disease fields that will be obtained include stone size (maximal axial and coronal dimensions), degree of hydronephrosis (mild/moderate/severe), and duration of prior ureteral stenting (if applicable).

Intra-operative data will include recording any buckling, kinking, or difficulty in instrument passage that occurs. Surgeons will be asked to subjectively rate the ease of sheath placement, stone extraction through sheath (if applicable), and ease of instrument passage on a scale 1 to 4, with 1 being poor and 4 being excellent. Ureteroscopic video will be taken for all procedures, and ureteral wall injuries will be evaluated after removal of the UAS by a urologist ([name]) blinded to the treatment device using the classification methodology previously described by Traxer and Thomas [3].

UAS related injuries determined by ureteroscopic video will be categorized into five (or 4 per PULS) grades, ranging from 0-4, defined by the following characteristics:

- Grade 0: No ureteral lesion or only mucosal petechiae
- Grade 1: Mucosal erosion or a mucosal flap without smooth muscle injury
- Grade 2: Damage to the mucosa and smooth muscle but no adventitia, with no retroperitoneal tissue visible
- Grade 3: Injury indicating ureteral perforation involving the full thickness of the ureteral wall, including the adventitia
- Grade 4: Total ureteral avulsion

Location of the primary injury site(s) (lumbar, iliac, pelvic ureter) will also be noted to determine impact on development of future pathology including stenosis, fistula or ureteral stone formation.

Perioperative fields will include OR (surgical) time, type of anesthesia, laser fiber size, guidewire specifications, need for dual lumen catheter or introducer catheter, settings of lithotripsy (if applicable - rate/energy), use of active extraction for fragments (include basket/grasper specifications), any device breakage or damage, and intraoperative complications.

All other procedures associated with standard of care for ureteroscopic treatment of stones, including stent placement, will be left to the discretion of the investigator. Postoperative fields will include postoperative complications, need for ancillary procedures, development or persistence of hydronephrosis/obstruction, and stone-free status at 4 to 6 week postoperative imaging as determined by ultrasound of kidneys, ureters and bladder.

Sample Size

A recent prospective study evaluating ureteral damage in 359 patients undergoing ureteroscopy with a 12/14F diameter sheath found that when using the same 5-point ureteral damage classification system, low grade ureteral injury (score of 0-1) occurred in 86.6% (311/359) of patients, and high grade (score of 2-4) occurred in 13.3% (48/359) of patients.

Based on this preliminary data, the study is powered to detect whether there is a difference between device designs to cause low (0-1) vs. high grade (2-4) ureteral injury. Using an alpha of 0.05 and beta of 0.80, and assuming a difference greater than 20% between groups is considered significant, approximately 49 patients will be required per arm, for a total of approximately 98 patients.

We are requesting the IRB allow for a total enrollment of 117 patients to account for screen failures (inability to gain access, rigid ureteroscopy required, strictures, etc).

Recruitment and Consent

Based on current volumes of ureteroscopic procedures, we anticipate approximately 2-3 patients per week will be randomized requiring a total of approximately 9-12 months of active enrollment between to reach a total of 100 randomized subjects. Patients will be recruited from either office visits or inpatient hospitalizations. The study coordinator will consent patients using the uploaded consent form accompanying this document. All procedures, devices and protocols are standard of care. There is no additional cost to the patient outside of standard care. The patient's insurance company will be billed for medical costs.

Data Analysis Plan

Data analysis will involve comparisons of ureteral damage between groups related to device design, gender, age, BMI, preoperative stenting, prior stone disease, and prior stone procedures. Differences in operative time, ease of placement, ability to maintain access, and ease of instrument passage will also be evaluated between devices, as well as post-operative complications, success rates, and device failure rates. The analysis will be completed by the approved researchers in coordination with a CCF biostatistician [name]. Study data will be stored on the RedCap database. Data may also be stored on encrypted CCF issued IronKey and encrypted CCF issued computers. Signed consent forms will be stored in a compartment with a lock for the duration of the trial. Approved researchers on this IRB will have access to these data.

Adverse Events and Data Monitoring Committee

The investigator will report any adverse events to the IRB within 10 days of awareness. A data monitoring committee will not be used. The primary risk to participants will be the loss of confidentiality, which will

be maintained by physical and electronic locks. Any unexpected findings of concern will be communicated face-to-face to the patient by the investigator in a clinic visit. A Data Monitoring Committee will not be used for this study as the devices and procedures used are standard care.

Study Costs

REFERENCES

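### Access and injury share one unranked primary objective, only injury is sized, and access failures are handled in three incompatible ways

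*Combined protocol and SAP*

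**What the plan says.** **Objective.** Purpose and Objectives states one primary objective with two parts, the ability of the two sheaths "to obtain and maintain access to the upper collecting system, as well as evaluate ureteral injury using standardized 5-point classification system". The secondary endpoints listed next are instrument passage, stone extraction, device placement and radiopacity. Neither obtaining nor maintaining access is among them.

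**Hypothesis.** The only one concerns safety: "We hypothesize that the modified designs of Re-Trace and Parallel devices will demonstrate similar safety profiles".

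**Sample Size.** Here "the study is powered to detect whether there is a difference between device designs to cause low (0-1) vs. high grade (2-4) ureteral injury". The error rates and effect size follow: "Using an alpha of 0.05 and beta of 0.80, and assuming a difference greater than 20% between groups is considered significant". The result is 49 per arm, 98 in total. No rate, difference or power is given for access.

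**Access failures.** Three statements apply to the same kind of patient:

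- Research method, on sheath diameter: "otherwise patients will be excluded from the study if unable to gain ureteral access".
- Research method, on backup sheaths: "If access has not been obtained after randomization to 6 sheaths, the patient will be considered a failure".
- Sample Size: a "total enrollment of 117 patients to account for screen failures (inability to gain access, rigid ureteroscopy required, strictures, etc".

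**Data Analysis Plan.** Ureteral damage comes first. Ability to maintain access then appears beside operative time and ease ratings, followed by success rates and device failure rates. No denominator, test, primary outcome or order of testing is given.

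**The concern.** Two things are left open.

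First, the plan does not say whether the primary result is injury, access, both together, or either one. A report could put either outcome forward as primary and cite the protocol for it.

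Second, and more serious, the access part of the objective has no settled denominator. Whether the assigned sheath gains access can be known only once it has been tried, so access failure happens after randomisation. Excluding such patients, or calling them screen failures, removes the very events that a comparison of obtained access needs. Counting failure only after a series of re-randomised sheaths keeps the patients but may credit one device with another's success.

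The same gap reaches injury. The plan does not say to which device an injury is attributed when a backup sheath was used, or whether a patient in whom access failed contributes an injury grade.

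**Working it through.** **1. The plan's own figures.** The reference high-grade rate is 48/359 = 13.37% (printed as 13.3%). With 98 patients that is 98 × 48/359 = 13.1 expected high-grade events. The enrolment allowance is 117 − 98 = 19 patients, or 19/117 = 16.2%; the plan does not say how many of these are access failures. The 49 per arm is taken as given. A two-sided test of 13.4% versus 33.4% at 80% power needs 70 per arm, and 49 gives 65.2% power. That is a separate matter, and nothing below depends on it.

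**2. What each access rule does to a device contrast.** The documents give no access rates. Assume first-sheath failure of 20% with device A and 10% with device B.

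- By first-assigned sheath, all randomised patients: 20% versus 10%, a contrast of 10 points.
- Access failures excluded: 0% versus 0% failure, so 100% versus 100% access. The contrast is 0 whatever the devices do.
- Failure counted after one backup: the answer depends on which device the backup is. The protocol says only that the patient is randomised to a backup sheath. It lists two devices but mentions three sheaths of 12/14F.

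| Backup sheath (assumed) | Failures independent | B failures all among A failures |
|---|---|---|
| Same device | 0.20² = 4% vs 0.10² = 1%: 3 points | 20% vs 10%: 10 points |
| Either device, 50:50 | 0.20 × 0.15 = 3% vs 0.10 × 0.15 = 1.5%: 1.5 points | 0.5 × 20% + 0.5 × 10% = 15% vs 10%: 5 points |
| Always the other device | 0.20 × 0.10 = 2% vs 0.10 × 0.20 = 2%: 0 points | 10% vs 10%: 0 points |

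Dilution is therefore likely but not certain, and its size cannot be derived from the documents. The plan's definition allows six sheaths, some of smaller diameter, which adds further mixing.

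**3. Precision for access as a secondary outcome.** The 95% half-width for a difference by first-assigned sheath is 1.96 × √(2p(1 − p)/n), assuming equal access p in both arms.

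- n = 49: 15.8, 11.9 and 8.6 points for p = 80%, 90% and 95%.
- n = 58 (if all 117 are randomised): 14.6, 10.9 and 7.9 points.

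**4. False-claim chance.** Take access as one outcome, with no true device difference.

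- Only injury counts, or both must succeed: no more than 5%.
- Either may count, each test at a full 5%: 1 − 0.95² = 9.75% if independent, 9.1% at correlation 0.5, 7.8% at 0.8. The upper bound is 0.05 + 0.05 = 10%.
- Either may count, Fisher's exact test on both, independent, 49 per arm: the actual size for injury at 13.37% is 2.16%. At assumed access-failure rates of 5%, 10%, 15% and 20%, the access size is 0.69%, 1.75%, 2.34% and 2.75%. Combined as 1 − (1 − 0.0216)(1 − size), the results are 2.8%, 3.9%, 4.4% and 4.9%.
- Access failures excluded: a test of obtained access at 100% versus 100% cannot reject, so it adds nothing.

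The plan names no test, so the range under an either-outcome rule is about 3% to at most 10%.

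**5. Cost of keeping both parts primary with a split alpha.** At 0.025 each, injury power with 49 per arm falls from 65.2% to 54.0%. The number needed for 80% power rises from 70 to 84 per arm.

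**The case against.** The best reply is that injury is plainly the lead outcome: the hypothesis is about safety, the sample size is for injury, and the analysis plan takes injury first. This is a fair inference and the reason the fix is easy. But it remains an inference, because the primary objective names access first and the list of secondary endpoints omits it.

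A second reply is that the analysis plan does include success rates and device failure rates, so access failures may be counted there. They may, but the denominator and the device to which each result belongs are still unstated.

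Some stronger readings are tempting, and the documents do not support them:

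- *The trial runs a 10% false-positive rate.* That needs a rule that either outcome can make the claim. No section states one, and even under it exact tests on both outcomes stay below 5% at the access rates examined. Nor can the exclusion reading and inflation from obtained access hold together.
- *Access cannot support any comparison.* The 100% argument covers obtaining access only. Maintaining it could still differ among patients in whom it was gained.
- *Backup sheaths erase any device difference.* That holds if the backup is always the other device, which the protocol does not say.
- *The injury comparison is faulty without stratification by preoperative stenting.* The analysis plan lists stenting among the factors by which damage is compared, but the documents give no prevalence or effect for it. The unadjusted randomised comparison is valid.

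**Conclusion.** The point holds as a minor one. The primary objective has two unranked parts and the design supports only injury. The three statements on access failure cannot all stand. Under the exclusion rule as written, the obtained-access part of the objective has no answer, because it is 100% in both arms. This follows from the text and needs no assumed rate. Under the six-sheath rule the result can mix devices; the size of the dilution (here from 10 points down to anywhere between 10 and 0 after one backup) rests on assumed failure rates, on how failures are related, and on which device the backup is.

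Multiplicity is the lesser part: about 3% to at most 10% under an unstated either-outcome rule, and no inflation if only injury counts or both are required. Nothing here invalidates the injury comparison itself, but its denominator and device attribution need stating.

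**What to change.** 1. Name high-grade (2-4) injury as the single primary outcome at alpha 0.05. This matches the existing hypothesis and sample size and needs no split of alpha.
2. Make access a key secondary outcome, reported with a 95% confidence interval for the device difference.
3. Reconcile the two Research method statements and the Sample Size statement on whether patients in whom access fails are excluded, failures or screen failures. This concerns the analysis population; how such patients are managed is not at issue here.
4. For analysis, keep every randomised patient in the denominator for obtained access and attribute the result to the first-assigned sheath. Results after backup sheaths can be reported descriptively.
5. Define maintained access separately, with its own denominator.
6. State the denominator and device attribution for injury in patients who received a backup sheath or in whom access failed.

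The cost is a protocol amendment, because the stated primary objective changes, and access loses formal primary status. No new data are needed, and multiplicity adds no patients. Stratifying injury by preoperative stenting repairs no error and is at most an optional sensitivity analysis.

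### The hypothesis is similarity, the sample size describes a test for a difference, and no test, interval or rule links the injury data to the hypothesis

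*Combined protocol and SAP*

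**What the plan says.** Three sections of the combined protocol and SAP bear on this.

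- **Hypothesis:** "We hypothesize that the modified designs of Re-Trace and Parallel devices will demonstrate similar safety profiles". This is the only hypothesis stated. It names no measure of safety and no margin.
- **Sample Size:** "the study is powered to detect whether there is a difference between device designs to cause low (0-1) vs. high grade (2-4) ureteral injury". The threshold and size follow: "assuming a difference greater than 20% between groups is considered significant, approximately 49 patients will be required per arm". The reference rate of high-grade injury is 13.3% (48/359).
- **Data Analysis Plan:** "Data analysis will involve comparisons of ureteral damage between groups related to device design" and by several patient characteristics. Post-operative complications appear only in a list: "as well as post-operative complications, success rates, and device failure rates". No test, interval, margin or success rule is given.

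Injury is not a side outcome. Purpose and Objectives puts it in the primary objective ("as well as evaluate ureteral injury using standardized 5-point classification system"), and it is the outcome that sets the sample size.

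**The concern.** A hypothesis of similarity and a test for a difference need different rules for reaching a conclusion. A difference test that fails to reject does not show that two devices are alike. That takes an interval narrow enough to exclude differences that matter. The plan states the first aim, describes the second, and gives no rule for either.

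The trial's main safety statement is at stake. A non-significant comparison whose interval still contains the plan's own 20-point difference could be reported as confirming the hypothesis, and nothing in the plan would stand against that report.

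**Working it through.** **Inputs.** From Sample Size: reference rate 13.3%, a 20% difference, alpha 0.05, a stated beta of 0.80, 49 per arm. Assumptions: the 0.80 is power, the 20% is in percentage points (so 13.3% versus 33.3%), and the test is two-sided.

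**Step 1. Where does 49 come from?**

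*Difference test as described* (pooled variance under the null, mean rate 0.233):

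n = [1.96·√(2·0.233·0.767) + 0.842·√(0.133·0.867 + 0.333·0.667)]² / 0.20² = [1.172 + 0.489]² / 0.04 = 68.9, about **69 per arm**.

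Other versions from the same rate also miss 49: 55 one-sided, 67 with unpooled variance and 68 by arcsine (53 one-sided for each of the last two).

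*Equivalence* (two one-sided 5% tests, margin ±20 points, both rates 13.3%, 80% power):

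n = 2·0.133·0.867·(1.645 + 1.282)² / 0.20² = 0.2306·8.564 / 0.04 = **49.4 per arm**.

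*Non-inferiority* with a 20-point margin gives 46 (one-sided 0.025) or 36 (one-sided 0.05).

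Of the calculations tried from the documents' 13.3%, only equivalence lands on the stated figure. A difference test of 5% versus 25% also gives 48.8, but neither rate is in the documents.

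**Step 2. Power at 49 per arm for the test described.**

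Standard errors: null √(2·0.233·0.767/49) = 0.0854; alternative √[(0.133·0.867 + 0.333·0.667)/49] = 0.0830.

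(0.20 - 1.96·0.0854)/0.0830 = 0.393, so power is **about 65%**. Exact enumeration gives 66% (chi-square) or 58% (Fisher).

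**Step 3. Does non-significance separate similar from inconclusive?**

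Examples with 49 per arm (chi-square p, Newcombe 95% CI in percentage points):

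| Events | p | 95% CI | Excludes 20 points? |
|---|---|---|---|
| 6 vs 13 | 0.07 | -1.5 to +29.5 | No |
| 6 vs 9 | 0.40 | -8.5 to +20.7 | No |
| 6 vs 8 | 0.56 | -10.2 to +18.4 | Yes |

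Exact binomial enumeration, 49 per arm. Ranges cover chi-square and Fisher tests, and Wald and Newcombe intervals:

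| True rates | Trials non-significant | Of those, 95% CI reaches 20 points |
|---|---|---|
| 13.3% vs 13.3% | 94-98% | 31-38% |
| 13.3% vs 33.3% | 34-42% | 92-94% |

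So a non-significant result often leaves the 20-point difference open even when the devices are identical, and nearly always does when they differ by that much.

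**Step 4. How much of this is sample size?** At 69 per arm and 13.3% versus 33.3%, 19-24% of trials are still non-significant, and in 86-89% of those the 95% CI still reaches 20 points. A larger trial shrinks the problem but does not supply the missing rule.

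**The case against.** The best defence is that the hypothesis is a plain statement of expectation. Such a sentence beside a difference test is common in short investigator-led protocols and is not in itself a contradiction. That is fair. A reader might infer that the plan intends to treat non-significance as proof of similarity. The documents do not support this: no sentence says so. What remains is the omission, since on either reading no rule is written for the outcome that sets the sample size.

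A second defence is that the study was really sized for equivalence and only worded badly. The 49.4 makes this plausible, and it is why the difference reading should not be preferred in advance. But a reader should not infer that equivalence is established. The text speaks of detecting a difference and never calls the 20% a margin, and the match is arithmetic only. If equivalence was meant, the margin and the rule still have to be written.

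Third, the 34-42% could be mistaken for the chance of a false similarity claim. It is the chance of a non-significant result, and part of it comes from the sample size. It should not be counted wholly as the cost of the missing rule.

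**Conclusion.** The concern holds as an omission together with a mismatch. The hypothesis, the sample size description and the analysis plan do not fit together, and nothing says what injury result would support similar safety. Reading non-significance as similarity is a risk that the plan leaves open, not a rule that it states.

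The size is material. With identical rates of 13.3%, about a third of non-significant trials (31-38%) would not exclude a 20-point difference. With 13.3% versus 33.3%, 92-94% would not. Separately, 49 per arm gives about 65% power for the difference test described, not 80%.

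These figures rest on reading 20% as percentage points and the stated beta as power, on a two-sided 0.05 test, and on 49 evaluable patients per arm. Using 48/359 unrounded changes little (70 rather than 69 per arm; 49.6 rather than 49.4). The sponsor should act on this, but it does not prevent the trial from running.

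**What to change.** The sponsor should say which aim was meant and make Hypothesis, Sample Size and Data Analysis Plan agree. Until then the two options rank equally.

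**(A) Difference.**
- Reword the hypothesis as a test of whether the proportion of patients with high-grade (2-4) injury differs between devices.
- Name one two-sided 0.05 test and the 95% CI that matches it, for example chi-square with the score interval from the same test. An unmatched pair can conflict: with Fisher and Newcombe at 13.3% versus 33.3%, about 8% of trials are non-significant while the interval excludes zero.
- Report the interval in all cases. State that a non-significant p-value is not evidence of similar safety, and that a non-significant result whose interval includes 20 points in either direction is inconclusive on that difference. An interval wholly within ±20 points supports only the statement that a difference of 20 points or more is excluded.
- Restate the power at 49 per arm for 13.3% versus 33.3% as about 65%.

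**(B) Equivalence.**
- Name ±20 points as the margin and justify it. It would tolerate a rate up to 13.3 + 20 = 33.3%.
- Conclude only that a difference of 20 points or more is excluded, and only when the 90% CI lies wholly inside the margin. Still report any significant difference as a difference.
- Acknowledge how wide the margin is: the rule would be met in about 21% of trials with true rates of 13.3% and 26.6% (an illustrative doubling, not a figure from the documents).

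**Both options.** State that the safety conclusion rests on high-grade injury and that post-operative complications are reported descriptively, or say how they enter it.

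**Cost.** A few sentences and no extra patients. The downside is that the trial may be inconclusive. If both rates are 13.3%, the 95% CI lies within ±20 points in 61-65% of trials, and the 90% CI in 76-80%. The wording does not cure the shortfall from 69 to 49 per arm under option A; it only discloses it.

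### The plan both excludes patients in whom ureteral access fails and counts them as failures, so the access result in the primary objective has no settled denominator

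*Combined protocol and SAP*

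**What the plan says.** **Objective.** Purpose and Objectives gives as the primary aim to "evaluate the ability for 2 different ureteral access sheaths to obtain and maintain access to the upper collecting system", together with grading ureteral injury.

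**Rule A, exclusion.** Research method, after allowing smaller diameters when there is resistance, continues: "otherwise patients will be excluded from the study if unable to gain ureteral access, or if ureteral balloon dilation or semi-rigid ureteroscopy is required". Sample Size treats the same events as screening losses, requesting "total enrollment of 117 patients to account for screen failures (inability to gain access, rigid ureteroscopy required, strictures, etc".

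**Rule B, failure.** Later in Research method the access attempts follow randomisation: "If unable to obtain access with the initial sheath the patient is randomized to, the patient will be randomized to a backup sheath". The sequence ends: "If access has not been obtained after randomization to 6 sheaths, the patient will be considered a failure". Balloon dilation is then one of the options left to the surgeon.

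**Analysis.** The Data Analysis Plan lists success and device failure rates among the comparisons between devices. It names no analysis population and no denominator, and does not say how a patient who moves to another sheath is counted.

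**Counts.** Sample Size requires about 98 patients and requests 117 enrolled. Recruitment and Consent aims for 100 randomised.

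**The concern.** A patient in whom no sheath passes is removed under Rule A and is a counted failure under Rule B. Because the first attempt uses the assigned sheath, failure to pass it can only be seen after randomisation. It therefore cannot be a screen failure in the usual sense. Read literally, Rule A removes randomised patients on the basis of an outcome in the primary objective.

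The level of the access result is at stake. Under Rule A everyone left in the analysis has access, so final access carries no information. First-sheath failures rescued by another sheath stay visible, while complete failures leave both numerator and denominator. Under Rule B the same data give a different answer. With no denominator fixed in advance, the choice could be made after the results are known.

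Two related points are also open. The protocol does not say whether the need for balloon dilation or semi-rigid ureteroscopy is established before or after randomisation. It also describes patients as "being randomized to the use of one of two ureteral access sheaths" but later writes "If unable to obtain access with any of the three sheaths with diameter 12/14F", so the pool of backup sheaths is not fully described.

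**Working it through.** **The plan's own figures.** There is no access failure rate, target or margin to reproduce. The only relevant figures are the counts:
- enrolled minus required: 117 − 98 = 19, to cover all listed reasons together
- enrolled minus randomised: 117 − 100 = 17
- randomised minus required: 100 − 98 = 2, or about 1 per arm

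**Formulas, per arm.** Let N be randomised, r the first-sheath failures rescued by another sheath, and f the complete failures.
- Final access: true (N − f)/N; under Rule A (N − f)/(N − f) = 100%.
- First-sheath failure: true (r + f)/N; under Rule A r/(N − f).
- Understatement: (r + f)/N − r/(N − f) = f(N − r − f)/[N(N − f)]. This is positive whenever f > 0 and at least one patient succeeds with the first sheath.

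**Level.** N = 50 follows from 100 randomised in two equal arms; r and f are assumed.

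| r | f | True first-sheath failure | Under Rule A | True final access | Under Rule A |
|---|---|---|---|---|---|
| 5 | 1 | 6/50 = 12.0% | 5/49 = 10.2% | 49/50 = 98% | 100% |
| 5 | 5 | 10/50 = 20.0% | 5/45 = 11.1% | 45/50 = 90% | 100% |

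The first row matches the planned counts, since 49 per arm remain, or 98 in all. The second leaves 90, below the 98 required.

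**Difference between arms in first-sheath failure.** Assumed r = 8 v 2, N = 50 per arm.

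| f | True | Under Rule A |
|---|---|---|
| 5 v 5 | 26.0% − 14.0% = 12.0 points | 8/45 − 2/45 = 13.3 points |
| 6 v 4 | 28.0% − 12.0% = 16.0 points | 8/44 − 2/46 = 13.8 points |
| 4 v 6 | 24.0% − 16.0% = 8.0 points | 8/46 − 2/44 = 12.8 points |

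With balanced complete failures the difference changes little. With an imbalance it can move either way.

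**Injury.** Assume 13.3% high grade in retained patients (the rate printed in Sample Size) and 30% to 40% in excluded patients (an assumption).
- At f = 5 v 5 the hidden difference is 0.
- At f = 6 v 4 and 30%: (44 × 0.133 + 6 × 0.30)/50 = 15.3% against (46 × 0.133 + 4 × 0.30)/50 = 14.6%, or 0.7 points.
- At f = 6 v 4 and 40%: 16.5% against 15.4%, or 1.1 points.

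These are small beside the 20-point difference in Sample Size.

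**The case against.** The strongest reply is that Rule B already counts these patients and the Data Analysis Plan intends device failure rates. On that reading nothing is lost. This stands to the extent that a reader who infers that the trial will necessarily report 100% access goes beyond the documents. It does not remove Rule A, which is also in the text and is repeated in Sample Size.

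A second reply is that the exclusions were meant to fall before randomisation. The counts support this: 17 of the 19 spare places lie between enrolled and randomised, leaving about 2 later losses. Background and Significance also separates guidewire access from sheath passage, so some access failures could precede sheath use. This is a fair reason to expect small numbers. But the exclusion sentence follows directly from resistance to advancing the sheath, and failure of an assigned sheath cannot come before assignment.

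A third reply is that this is a comparative trial and the comparison may be little affected. That largely stands. Complete failures pass through backup sheaths, at least partly in random order, and may be roughly balanced between arms. A reader might infer a biased device comparison; the documents do not show one, and the larger shifts above come from chosen imbalances. Balance is not assured either, because the backup pool is unclear and Rule A does not require six failed sheaths before a patient is excluded for dilation.

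Finally, final access with any sheath is not a named endpoint, and success after several sheaths does not measure the assigned device. That is a reason to make first-sheath access the main access result.

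**Conclusion.** The contradiction is real and concerns part of the primary objective. Its consequences are conditional. If the exclusion governs, final access is 100% in both arms whatever the devices do, and first-sheath failure is understated whenever a complete failure occurs. If the failure rule governs, with those patients kept in the denominator, neither follows.

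The size cannot be fixed from the documents. With about one complete failure per arm, as the planned counts suggest, the understatement in the assumed example is 1.8 points (12.0 − 10.2). With five per arm it is 8.9 points (20.0 − 11.1), but that fits the counts poorly. The finding rests on the level of the access result and on the missing denominator, not on a demonstrated difference between arms. The effect on the injury comparison is probably small.

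**What to change.** For the analysis, reconcile the two rules in Research method with Sample Size:

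- State when randomisation takes place, and which of 98, 100 and 117 are evaluable, randomised and enrolled.
- Limit screen failure to ineligibility found before randomisation.
- Analyse access in all randomised patients by first assigned sheath. Failure to gain access with that sheath counts as an access failure for it, even when a backup or smaller sheath, dilation or semi-rigid ureteroscopy follows.
- Report final access with any sheath separately, with all randomised patients in the denominator.
- Record the sheaths tried, in order, with the result of each.
- Because "Ureteroscopic video will be taken for all procedures, and ureteral wall injuries will be evaluated after removal of the UAS", report per arm how many randomised patients have no injury grade.

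The cost is protocol wording, one data field and a little more analysis. Slightly fewer patients may be evaluable for injury. If 100 are randomised and 5 per arm have no grade (assumed), the 95% half-width for a difference, 1.96 × √(2 × 0.133 × 0.867/n), goes from 13.4 points at n = 49 to 14.0 at n = 45. No change to the clinical management of failed access is proposed.
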